1.3. Sample Size and Power

Sample size and power are estimated for the co-primary endpoints with the overall alpha level 0.05 (with alpha = 0.04 allocated to the development of a LRTC and alpha = 0.01 allocated to the time-weighted average change in viral load). The sample size calculations are based on the results observed in a study that evaluated the efficacy of oral and aerosolized ribavirin treatment for preventing progression from upper to lower respiratory tract infection in HCT recipients with RSV infections (unpublished data from [name]) and published data on currently used antiviral agents for RSV infections. {Shah 2013}

Assuming the time-weighted average change in RSV log₁₀ viral load from Day 1 to Day 9 in the placebo group will be -1 log₁₀ copies/mL, with a standard deviation (SD) of 2, 100 subjects per treatment group will provide over 80% power to detect at least 1 log₁₀ decrease in presatovir group using a 2-sided significance level of 0.01.

Assuming that 30% of subjects in placebo arm will develop a LRTC, 100 subjects per treatment group will provide over 90% power to detect at least 20% reduction in the proportion of LRTC in presatovir group with a 2-sided significance level of 0.04.

Using the fallback approach and the above assumptions for the co-primary endpoints, 100 subjects per arm will provide > 95% power to declare statistical significance in either change in viral load or proportion of subjects with LRTC.

Based on an administrative review of the data occurring in mid-September 2017, Gilead decided to halt the study on 20September2017 at an enrollment of 189 subjects despite the study not achieving complete enrollment of 200 subjects. The decision was made because enrollment of the remaining 11 subjects would have had minimal impact on study outcomes.

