3.5. Multiple Comparisons

This study has 2 co-primary endpoints: the time-weighted average change in RSV log₁₀ viral load from Day 1 to Day 9, and the proportion of subjects who develop a LRTC through Day 28. To control the Type 1 error rate of 0.05 across the co-primary and secondary endpoints, a fallback approach will be applied {Wiens 2005} {Dmitrienko 2008} (see Figure 3-1).

The time-weighted average change in RSV log₁₀ viral load from Day 1 to Day 9 will be tested first at significance level of 0.01. If this null hypothesis (H₀₁) of no difference between the treatment groups is rejected then the proportion of subjects who develop an LRTC (H₀₂) will be tested with significance level of 0.05. Otherwise, the null hypothesis of no difference between treatment groups in the proportion of subjects who develop an LRTC will be tested at significance level of 0.04.

If both of the co-primary null hypotheses (H₀₁ and H₀₂) are rejected then the secondary endpoint will be tested at a significance level of 0.05. If only the null hypothesis of no difference between treatment groups in the proportion of subjects who develop an LRTC (H₀₂) is rejected, the secondary endpoint will be tested at a significance level of 0.04. If the hypothesis H₀₂ is not rejected then the secondary endpoint will not be tested.

Figure 3-1. Testing of Co-primary and Secondary Endpoints

- a Co-primary endpoint: Time-weighted average change in log₁₀ viral load
- b Co-primary endpoint: Proportion of subjects who developed LRTC
- c Secondary endpoint: Proportion of subjects who either developed respiratory failure (of any cause) requiring mechanical ventilation (invasive or non-invasive) or died prior to or on Day 28

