6.2.1. Time-Weighted Average Change in Nasal RSV Viral Load

The treatment difference in the time-weighted average change from Baseline (Day 1) to Day 9 in nasal RSV viral load (\log_{10} copies/mL) will be analyzed using a parametric ANCOVA with the baseline viral load (\log_{10} copies/mL) and stratification factors as covariates in the model. The test will be 2-sided with the significance level of 0.01. Nonparametric methods such as rank-based ANCOVA models or Wilcoxon rank sum tests may be implemented for exploratory purposes.

Adjusted means for each treatment group, 99% confidence interval (CI), and descriptive statistics (sample size, mean, SD, median, Q1, Q3, minimum, and maximum) will be presented in the descriptive summaries. Missing viral load data will be handled using the method described in Section 3.6.

6.2.2. Proportion of Subjects Who Develop a LRTC through Day 28

The proportion of subjects who develop a LRTC through Day 28 will be analyzed using a 2-sided Cochran-Mantel-Haenszel test stratified by the randomization stratification factors. The significance level used for the analysis (eg, 0.04 or 0.05) will be determined based upon the decision to reject the null hypothesis of the other co-primary endpoint as described in Section 3.5. The 2-sided 95% CI for the odds ratios between the 2 treatment groups will be constructed based on stratum-adjusted Mantel-Haenszel proportions.

The numbers and percentages of subjects who develop a LRTC through Day 28 will be provided with 95% CIs for the percentages based on the Clopper-Pearson method {Clopper 1934}.

The final analysis will be performed when all randomized subjects either complete Day 28 assessments or discontinue study prematurely.

The analyses of the co-primary endpoints will be repeated using the PP analysis set.

The primary efficacy analyses will also be repeated for the subgroups specified in Section 3.4, including the stratification factors (presence or absence of lymphopenia, treatment of RSV infection with ribavirin [yes or no] prior to randomization, sex, race, age group [< 65 or ≥ 65], type of transplant [autologous HCT or allogeneic HCT]. Adjusted mean and 95% CI will be presented by treatment group for exploratory purposes.

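### The odds-ratio intervals for LRTC and the secondary endpoint use a construction that need not match the stratified CMH test, and stay at 95% even when the test is at 0.04

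*SAP*

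**What the plan says.** SAP 6.2.2 says LRTC through Day 28 will be "analyzed using a 2-sided Cochran-Mantel-Haenszel test stratified by the randomization stratification factors". On the level it says: "The significance level used for the analysis (eg, 0.04 or 0.05) will be determined based upon the decision to reject the null hypothesis" for viral load. The effect estimate follows: "The 2-sided 95% CI for the odds ratios between the 2 treatment groups will be constructed based on stratum-adjusted Mantel-Haenszel proportions". Protocol 8.5.1 carries the same interval sentence, and SAP 6.3.2 repeats it for respiratory failure or death. Protocol 8.5.2 gives no interval for that secondary endpoint.

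The levels come from the fallback procedure in SAP 3.5 and Protocol 8.5:

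- Viral load (H01) is tested at 0.01.
- LRTC (H02) is tested at 0.05 if H01 is rejected. Otherwise, "the proportion of subjects who develop an LRTC will be tested at significance level of 0.04".
- If both are rejected, the secondary endpoint is tested at 0.05. If only H02 is rejected, "the secondary endpoint will be tested at a significance level of 0.04". If H02 is not rejected, it is not tested.

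For viral load the plan uses a 99% interval beside its 0.01 test. No readable text names the Mantel-Haenszel common odds ratio or a variance for it, explains how adjusted proportions become an odds ratio, or calls the 95% interval descriptive. SAP 6.5, on changes from the protocol's efficacy analyses, is blacked out.

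**The concern.** There are two mismatches between the interval and the test.

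The first is the estimator. Mantel-Haenszel-weighted proportions are averages of stratum risks. They lead directly to a stratified risk difference. An odds ratio can be taken from them, but it is a marginal one. The Mantel-Haenszel common odds ratio is built from within-stratum cross-products and has its own variance. Two programmers following the sentence could report different odds ratios for a co-primary endpoint.

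The second is the level. A two-sided test at 0.04 corresponds to a 96% interval. With 95% fixed on both branches, a report could show an odds-ratio interval that excludes 1 beside a hypothesis formally not rejected. Readers will quote the odds ratio and its interval, so the two should tell the same story.

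**Working it through.** **Inputs.** From SAP 1.3: placebo LRTC rate 30%, a 20-point reduction, 100 per arm, two-sided alpha 0.04 for LRTC; viral-load difference 1 log10, SD 2, alpha 0.01; 189 enrolled, so 189/2 = 94.5 per arm. Stratum tables below are assumptions, because the documents give no stratum sizes or risks.

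**The plan's own power figures.** For proportions, power = Φ{[δ√n − z√(2p̄q̄)] / √(p₁q₁ + p₀q₀)}. With n = 100 and 30% v 10%: (0.20 × 10 − 2.054 × 0.566)/0.548 = 1.530, so power is 93.7%, which meets the stated figure of over 90%. (A 20% relative reduction, 30% v 24%, would give 13.6%, so the plan means 20 points.) Viral load: 1/(2√(2/100)) − 2.576 = 0.960, so power is 83.1%, which meets over 80%.

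**Estimator.** With a/n₁ events on presatovir and c/n₀ on placebo in each stratum, b = n₁ − a, d = n₀ − c and N = n₁ + n₀:

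- Common odds ratio = Σ(ad/N) / Σ(bc/N).
- Adjusted proportions use weights n₁n₀/N. Their odds ratio is [p₁/(1 − p₁)] / [p₀/(1 − p₀)].

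Three assumed two-stratum tables, presatovir v placebo:

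- *Equal rates*, 2/20 v 6/20 and 8/80 v 24/80: both methods give 0.259 (95% CI 0.119 to 0.566).
- *Milder differences*, 5/20 v 11/20 and 5/80 v 19/80: common odds ratio (1.125 + 1.906)/(4.125 + 8.906) = 0.233 (0.102 to 0.529). Adjusted proportions are 0.10 and 0.30, odds ratio 0.259 (0.122 to 0.551).
- *Strong differences*, 12/20 v 16/20 and 4/80 v 14/80: common odds ratio (1.20 + 1.65)/(3.20 + 6.65) = 0.289 (0.119 to 0.706). Adjusted proportions are 0.16 and 0.30, odds ratio (0.16/0.84)/(0.30/0.70) = 0.444 (0.254 to 0.777).

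Unequal stratum risks are plausible. Ribavirin treatment is a stratification factor, and Protocol 1.1 cites a retrospective analysis with progression of 16% in treated and 45% in untreated patients. If those were the placebo risks in two equal strata with a common odds ratio of 0.26, the presatovir risks would be 4.7% and 17.5%. The averages are 11.1% v 30.5%, and the odds ratio from them is 0.285.

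**Level.** z(0.98)/z(0.975) = 2.054/1.960 = 1.048, so the 96% interval is 4.8% wider on the log scale. Take 18/100 v 30/100 as a single stratum:

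- CMH chi-square = (18 − 24)²/9.166 = 3.928, p = 0.0475: not significant at 0.04.
- Odds ratio = (18/82)/(30/70) = 0.512. SE of its log = √(1/18 + 1/82 + 1/30 + 1/70) = 0.340.
- 95% CI 0.263 to 0.997, which excludes 1. 96% CI 0.255 to 1.029, which includes 1.

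**How often.** The chance of 0.04 < p < 0.05 is the power at 0.05 minus the power at 0.04. At 94.5 per arm this is 1.3% for 30% v 10%, 3.4% for 30% v 15%, 3.8% for 30% v 17% and 3.4% for 30% v 20%.

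The conflict also needs H01 not to be rejected. At 94.5 per arm, 1/(2√(2/94.5)) − 2.576 = 0.861, power is about 81%, and non-rejection is about 19% (17% at 100 per arm). If the endpoints are independent, the joint chance runs from 1.3% × 0.19 = 0.2% to 3.8% × 0.19 = 0.7%. If presatovir has little viral effect, H01 is almost never rejected and the chance approaches 1.3% to 3.8%.

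**The case against.** The strongest reply is that no decision rests on an interval. The fallback procedure works on p-values, so a conventional 95% interval is a reporting choice that needs at most a descriptive label. This stands as to consequences: a reader might infer that type I error or power is compromised, and the documents do not support that. It does not explain why viral load has an interval matched to its alpha while LRTC does not.

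Next, an odds ratio can legitimately be formed from adjusted proportions. SAP 6.2 words H02 as a difference in proportions, and the CMH null of no association within strata does not require a common odds ratio. So the estimator should not be called impossible. The fair criticism is that it is not the usual companion of CMH, can differ from it, and has no stated variance.

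Third, a Wald-type interval is not an exact inversion of CMH. With 16/94 v 28/94, p = 0.0393, which rejects at 0.04, yet the upper 96% limit is 1.003. Matching the level removes the systematic conflict but not every disagreement near the boundary.

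Two further readings go too far. A reader might infer that the secondary endpoint is tested at 0.04 whenever H01 is not rejected; SAP 3.5 also requires H02 to be rejected. A reader might also infer that the 99% viral-load interval in SAP 6.2.1 covers only the group means and not the treatment difference. That sentence is a list whose punctuation settles nothing, so it supports no criticism.

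**Conclusion.** The point holds, with modest consequences. The interval rule for a co-primary endpoint and the secondary endpoint does not specify the odds ratio normally paired with the stratified CMH test, and its level is wrong for the test on the 0.04 branch. On the 0.05 branch, 95% is correct.

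The estimator gap is nil when event rates are equal across strata. It ranged from 0.259 v 0.233 to 0.444 v 0.289 in the assumed tables, and its size in this trial cannot be known from the documents. The 0.2% to 0.7% chance of the level conflict rests on the design's viral-load effect and SD, independent endpoints, a normal approximation, and all 189 enrolled subjects entering the analysis. The full analysis set may be smaller.

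**What to change.** In SAP 6.2.2 and 6.3.2, and for consistency Protocol 8.5.1:

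- Report the Mantel-Haenszel common odds ratio with a Robins-Breslow-Greenland interval. Optionally add the stratum-adjusted Mantel-Haenszel risk difference with its own interval, labelled as such.
- For LRTC, set the level to 1 minus the alpha actually used: 96% if H01 is not rejected, 95% if it is.
- For the secondary endpoint, use 96% only when H01 is not rejected and H02 is rejected, and 95% when both are rejected. When it is not formally tested, give a 95% interval labelled descriptive.

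The cost is a few sentences and standard software options. Sample size and the CMH test do not change. The downside is that intervals on the 0.04 branch are 4.8% wider on the log scale, and rare near-boundary disagreement with CMH remains.

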6.3. Secondary Efficacy Endpoints

6.3.1. Definition of Secondary Efficacy Endpoint

Secondary efficacy endpoint is the proportion of subjects who develop respiratory failure requiring mechanical ventilation or died from any cause through Day 28.

Subject will be considered to have an event if either condition is met if subject develops:

- A respiratory failure (of any cause) requiring mechanical ventilation (invasive or noninvasive) or
- All-cause mortality through Day 28.

6.3.2. Analysis Methods for Secondary Efficacy Endpoint

A sequential fallback testing procedure described in Section 3.5 will be used to control the overall Type 1 error rate of 0.05 across the primary and secondary endpoints.

The FAS analysis set will be used for all summaries and analyses of the secondary endpoint. Treatment groups will be compared using a 2-sided test.

The proportion of subjects who develop respiratory failure requiring mechanical ventilation or all-cause mortality through Day 28 will be analyzed using a Cochran-Mantel-Haenszel test stratified by the randomization stratification factors. The 2-sided 95% CI for the odds ratios between the 2 treatment groups will be constructed based on stratum-adjusted Mantel-Haenszel proportions.

If the number of events is small then the exact method will be applied.

The numbers and percentages of subjects who meet the secondary endpoint criteria, who develop respiratory failure requiring mechanical ventilation and who have all-cause mortality through Day 28 will be provided. The 95% CIs for the percentages will be calculated using the Clopper-Pearson method {Clopper 1934}.

6.3.3. Sensitivity Analysis for Secondary Efficacy Endpoint

Sensitivity analyses of the secondary efficacy endpoint, the proportion of subjects who develop respiratory failure requiring mechanical ventilation or all-cause mortality through Day 28, will be performed in the PP analysis set.

6.4. Exploratory Efficacy Endpoints

6.4.1. Definition of Exploratory Efficacy Endpoints

PPD [REDACTED]

- [REDACTED]
- [REDACTED]
- [REDACTED]
- [REDACTED]
- [REDACTED]
- [REDACTED]
- [REDACTED]
- [REDACTED]
- [REDACTED]
- [REDACTED]
- [REDACTED]
- [REDACTED]
- [REDACTED]
- [REDACTED]
- [REDACTED]
- [REDACTED]
- [REDACTED]
- [REDACTED]

6.4.2. Analysis Methods for Exploratory Efficacy Endpoints

PPD

[Redacted]

[Redacted]

[Redacted]

[Redacted]

[Redacted]

[Redacted]

PPD

[Redacted]

[Redacted]

[Redacted]

[Redacted]

[Redacted]

[Redacted]

[Redacted]

[Redacted]

6.5. Changes From Protocol-Specified Efficacy Analyses

PPD [Redacted]

[Redacted]

[Redacted]

[Redacted]

[Redacted]

[Redacted]

[Redacted]

[Redacted]

[Redacted]

[Redacted]

[Redacted]

[Redacted]

[Redacted]

[Redacted]

[Redacted]

[Redacted]

7. SAFETY ANALYSES

7.1. Adverse Events and Deaths

7.1.1. Adverse Event Dictionary

Clinical and laboratory AEs will be coded using the current version of the Medical Dictionary for Regulatory Activities (MedDRA). System organ class (SOC), high level group term (HLGT), high level term (HLT), preferred term (PT), and lower level term (LLT) will be attached to the clinical database.

7.1.2. Adverse Event Severity

Adverse events are graded by the investigator as Grade 1 (mild), Grade 2 (moderate), Grade 3 (severe), or Grade 4 (life-threatening) according to toxicity criteria specified in the protocol. The severity grade of events for which the investigator did not record severity will be categorized as “missing” for tabular summaries and data listings. The missing category will be listed last in summary presentation.

7.1.3. Relationship of Adverse Events to Study Drug

Related AEs are those for which the investigator selected “Related” on the AE eCRF to the question of “Related to Study Treatment.” Relatedness will always default to the investigator’s choice, not that of the medical monitor. Events for which the investigator did not record relationships to study drug will be considered related to study drug for summary purposes. However, by-subject data listings will show the relationship as missing.

7.1.4. Serious Adverse Events

Serious adverse events will be identified and captured as SAEs if AEs met the definitions of a SAE specified in the study protocol. Serious adverse events captured and stored in the clinical database will be reconciled with the SAE database from the Gilead Drug Safety and Public Health Department before database finalization.

7.1.5. Treatment-Emergent Adverse Events

7.1.5.1. Definition of Treatment-Emergent Adverse Events

Treatment-emergent adverse events are defined as one or both of the following:

- Any AEs with an onset date on or after the study drug start date and no later than visit Day 28, or up to 28 days if a subject withdraws early (prior to Day 28) from the study
- Any AEs leading to premature discontinuation of study drug.

7.1.5.2. Incomplete Dates

If the onset date of the AE is incomplete, then the month and year (or year alone if month is not recorded) of onset determine whether an AE is treatment emergent, as long as the AE stop date is not prior to the first dosing date of study drug. The event is considered treatment emergent if either of the following 2 criteria is met:

- The AE onset and end dates are the same as or after the month and year (or year) of the first dosing date of study drug
- The AE onset date is the same as or before the month and year (or year) of the Day 28 visit

An AE with completely missing onset and stop dates, or with the onset date missing and a stop date later than the first dosing date of study drug, will be considered to be treatment emergent.

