Subjects with upper respiratory tract infections who screened under the GS-US-218-1502 protocol, and who did not qualify due to absence of lower respiratory tract infection via sample or X-ray may be screened for the GS-US-218-0108 study. In these cases, screening procedures completed for the GS-US-218-1502 study may be used in support of the GS-US-218-0108 Screening Visit. Subjects who screened for GS-US-218-0108 but who show new signs of lower respiratory tract infection via chest X-Ray, may screen fail from GS-US-218-0108 and screen into GS-US-218-1502.

Subjects meeting all of the inclusion criteria and none of the exclusion criteria will return to the clinic after screening for randomization into the study. Subjects must continue to meet all inclusion criteria and none of the exclusion criteria at the time of randomization. If all lab results and procedures are available and satisfy the inclusion/exclusion criteria, Screening and Visit 2 (Day 1) may occur on the same day.

From the time of obtaining informed consent through the first administration of IMP, record all SAEs, as well as any AEs related to protocol-mandated procedures on the AE case report form (eCRF). All other untoward medical occurrences observed during the Screening period, including exacerbation or changes in medical history are to be captured on the medical history eCRF. See Section 7 Adverse Events and Toxicity Management for additional details.

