- e Central laboratory testing: hematology and serum chemistry to include WBC with differential, Hgb, platelets, BUN, creatinine, serum albumin, AST, ALT, ALP, and TB
- f 2 samples total, 1 from each nostril – collected prior to dosing on dosing days.
- g For subjects in the PK subgroup only: Collected 1 (±15 min), 2 (±15 min), 4 (±30 min) and 6 hours (±30 min) post-dose
- h For all subjects: collected pre-dose on Day 5, pre-dose and 2 hours (±15 min) post-dose on Day 9, and anytime on Day 22

- i For subjects in the PK subgroup only: PK is collected anytime during Visit 3 and Visit 3 must occur in clinic.
- j For subjects in the PK subgroup only. Subjects not participating in the PK subgroup can have this visit completed at home by a home nursing vendor or by the study coordinator or designee.
- k For subjects in the PK subgroup only: Blood draw for serum creatinine 2 hours (\pm 15 min) post dose on Day 1 and Day 9 (Visit 2 and Visit 6)
- l Only for subjects who agree to the optional extended viral monitoring at the time of consent.
- m Only for subjects who agree to the optional extended viral monitoring at the time of consent and test positive (or inconclusive) for RSV at Visit 9 (Day 22)
- n Assessment of procedure-related AEs only, if home visit
- o Not required if home visit
- p Local troponin testing will be done pre-dose in accordance with the standard assay available and used at the site. Point-of-care “rapid” troponin tests are not acceptable for protocol-mandated troponin testing.
- q Visit 3: Day 3 is an optional study visit for subjects not participating in the PK subgroup.
- r For Japan sites only, 2 nasal swab samples will be obtained at Screening, 1 for local RSV testing and 1 for testing at the central laboratory. At Baseline, only 1 sample will be obtained for central laboratory testing.
- s Subjects who were not tested for RSV as standard of care may consent to the study and be tested subjects for RSV during the Screening visit.

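### SAP 7.1.5.2 accepts either bound of the treatment-emergent window where both are needed, so for a partial onset date with a known end date the recorded month or year excludes nothing

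*SAP*

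**What the plan says.** SAP 7.1.5.1 defines a treatment-emergent AE by date with two bounds: "Any AEs with an onset date on or after the study drug start date and no later than visit Day 28". For a subject who withdraws before Day 28 the upper limit is given as up to 28 days. A second route ignores the onset date: "Any AEs leading to premature discontinuation of study drug". Protocol 8.6.2 also bounds the period on both sides.

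SAP 7.1.5.2 covers incomplete onset dates. The recorded month and year, or the year alone, are to decide the matter, "as long as the AE stop date is not prior to the first dosing date of study drug". It then says "The event is considered treatment emergent if either of the following 2 criteria is met", and lists:

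- criterion 1: "The AE onset and end dates are the same as or after the month and year (or year) of the first dosing date";
- criterion 2: "The AE onset date is the same as or before the month and year (or year) of the Day 28 visit".

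A closing paragraph of 7.1.5.2 counts an AE as treatment-emergent when onset and stop dates are both completely missing, or when onset is missing and the stop date is after first dose. SAP 7.7 declares no change from the protocol's safety analyses, so nothing marks the partial-date rule as a deliberate departure.

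**The concern.** Criterion 1 is the lower edge of the 7.1.5.1 window and criterion 2 is the upper edge. An event lies inside the window only if it satisfies both. Joined by *either*, an event known to start after the Day 28 month can qualify through criterion 1, and an event known to start before the first-dose month qualifies through criterion 2.

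The same event can then be classified differently according to how completely its date was recorded. With a full date after the Day 28 visit it is not treatment-emergent by date. With the day missing and the month still known to be after the Day 28 month, it is. The flag feeds the tables in SAP 7.1.6.1, including those for all TEAEs, Grade 3 or higher events, treatment-related events and serious events.

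**Working it through.** The plan states no figure here to reproduce. The check is one of logic.

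**Notation.** F is the first-dose month, D the Day 28 month, O the recorded onset month and E the end month (read as years when only the year is known). Day 28 is first dose plus 27 days, so D ≥ F.

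- Criterion 1: O ≥ F and E ≥ F.
- Criterion 2: O ≤ D.
- Proviso: the stop date is not before first dose.

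**Known end date.** Suppose criterion 2 fails. Then O > D ≥ F. An event cannot end before it starts, so E ≥ O > F and criterion 1 holds. At least one criterion is therefore always met, and the proviso alone decides.

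**Missing or ongoing end date.** If O ≤ D, criterion 2 is met. If O > D, the result depends on criterion 1, which refers to an end date and does not say how a missing one is read.

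**Enumeration.** The rule was applied to every first-dose date in 2016 (366), onset from 60 days before to 90 days after first dose (151 offsets), and event durations of 0, 3, 10, 40 and 80 days. That gives 366 × 151 × 5 = 276,330 cases with a known end date. Onset was reduced to month and year.

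| Onset month | Cases | Meet either criterion | Treatment-emergent under *either*, after proviso | Treatment-emergent under *both*, after proviso |
|---|---|---|---|---|
| Before first-dose month | 82,795 | 82,795 | 26,530 | 0 |
| First-dose to Day 28 month | 105,250 | 105,250 | 93,073 | 93,073 |
| After Day 28 month | 88,285 | 88,285 | 88,285 | 0 |

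The 26,530 are exactly the earlier-month cases whose stop date is on or after first dose. Year-only onsets with a known end date also meet one criterion in every case.

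With no end date (366 × 151 = 55,266 cases), *either* flags all 16,559 earlier-month cases and all 21,050 in-window cases. It flags all 17,657 later-month cases if a missing end date is read as after first dose, and none if it is read as failing criterion 1. On that second reading, *both* would flag 0 of the 21,050 in-window cases.

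The grid is uniform. The counts show how the rule behaves and are not expected frequencies in the trial.

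**Illustration (dates assumed).** First dose is 1 March, so Day 28 is 28 March and the Day 17 last dose is 17 March. Protocol 7.3 asks for SAEs and deaths within 30 days or 4 weeks of the last dose; 30 days runs to 16 April. An SAE dated 10 April falls outside 7.1.5.1. The same SAE recorded only as April, with a known end date, meets criterion 1 and is flagged.

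**Which events can reach the data.**

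- After Day 28: SAEs and deaths under Protocol 7.3, later SAEs deemed relevant to study drug, and procedure-related AEs at Visits 11–14 (Days 35 to 56).
- Before dosing, the AE form is restricted: "From the time of obtaining informed consent through the first administration of IMP, record all SAEs, as well as any AEs related to protocol-mandated procedures". Screening is nominally Day -1, so an earlier-month onset needs a screening period that crosses a month boundary.

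**The case against.** The strongest reply is that little follows from the slip and that a careless repair would be worse. Much of this stands.

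- A reader might infer that every partial date passes. The documents do not support that. The proviso still removes events that stopped before first dose, and an onset after the Day 28 month with no end date may fail both criteria.
- A reader might infer that events from months before dosing enter the tables. Protocol 7.1.1 treats a condition with onset before consent, unless related to a protocol procedure, as medical history and not an AE. Only the screening-period events described above remain.
- A reader might infer an imbalance between arms, because Visits 11–14 are for consenting subjects still RSV-positive or inconclusive at Day 22, a status that an effective antiviral could change. That chain also needs an AE, a partial onset date and a later calendar month, and no figure in the documents supports it. Procedure causality is assessed separately from drug causality (Protocol 7.2.1), and the related-AE tables use the study-treatment question (SAP 7.1.3).
- Replacing one word would not be enough. Criterion 1 asks for an end date, so a bare *both* could drop ongoing events that belong in the window. Subjects who withdraw early may have no Day 28 visit for criterion 2.

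It can also be said that over-inclusion is conservative and matches neighbouring rules, such as counting missing causality as related. That does not rescue *either*. Conservatism is for unknown timing, and here the recorded month places the event outside the window. For concomitant medications, SAP 7.4.2 excludes partial dates whose known month or year is outside the period. Requiring both criteria still keeps every known-end event in an overlapping month that passes the proviso.

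**Conclusion.** Wrong as written. Followed exactly, SAP 7.1.5.2 makes the recorded onset month or year irrelevant for any partial-onset AE with a known end date that passes the stop-date proviso. This contradicts SAP 7.1.5.1 and Protocol 8.6.2, and no other section corrects it.

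The practical size is probably small. The documents do not give the number of partial-date AEs, and the main route is a late-reported event whose known onset month is after the Day 28 month. Only descriptive TEAE summaries are affected; no efficacy test, alpha or sample size depends on the flag. All AEs are listed with their treatment-emergent status (SAP 7.1.6.1), so a wrong flag can be traced. The conclusion assumes that the program follows the SAP text literally. The documents do not show the program.

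**What to change.** Revise SAP 7.1.5.2 in three respects:

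1. Require that both criteria are met, in place of either one.
2. State that an ongoing or missing end date counts as on or after first dose, so that ongoing in-window AEs are kept.
3. For subjects who withdraw before Day 28, use the same upper limit as in SAP 7.1.5.1 in place of the Day 28 visit.

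Leave the separate route for AEs leading to discontinuation of study drug unchanged. Then check that the derivation program matches the revised text. The cost is one changed sentence, two short additions and a check of one derived flag; no further data are needed.
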